## 2. Study Design

### A. Overview

This study is a prospective, multi-center, single-arm, non-randomized study enrolling subjects with lifestyle-limiting claudication or ischemic rest pain attributable to lesion(s) (stenosed, occluded, restenosed, or re-occluded) in the infra-inguinal segment (superficial femoral artery (SFA) and/or proximal popliteal artery) that are amenable to treatment by percutaneous transluminal angioplasty (PTA) and stenting. Investigators should select an appropriately sized device(s) to treat subjects with target lesion(s) up to 240 mm. Clinical follow-up for all subjects will be performed at hospital discharge, 30-days and 12-, 24-, and 36-months post-procedure.

### B. Study Population

The study population will consist of subjects with lifestyle-limiting claudication or ischemic rest pain attributable to lesion(s) (stenosed, occluded, restenosed, or re-occluded) in the infra-inguinal segment (SFA) and/or proximal popliteal artery) that are amenable to treatment by PTA and stenting. The reference vessel diameter must be  $\geq 4.0$  mm and  $\leq 6.5$  mm.

A minimum of 234 subjects will be enrolled at up to 25 sites throughout the United States.

### C. Sample Size Determination

The protocol includes sample size considerations for the primary safety endpoint, the primary effectiveness endpoint and two secondary effectiveness endpoints (freedom from TLR/TVR through 12-months post-index procedure, and secondary device success). The secondary effectiveness (device success) endpoint required the largest sample size based on the following considerations:

*Objective: To demonstrate that device success (combined acute and chronic effectiveness) in the CONTINUUM LifeStent® group is not inferior to the observed device success of the RESILIENT12 LifeStent® group at 12-months post-index procedure.*

H0: The device success rate at 12-months post-index procedure with CONTINUUM LifeStent® (PCONTINUUM) is inferior to the device success rate with RESILIENT12 LifeStent® (PRESILIENT).

H1: The device success rate at 12-months post-index procedure with CONTINUUM LifeStent® (PCONTINUUM) is not inferior to the device success rate with RESILIENT12 LifeStent® (PRESILIENT).

H0: PCONTINUUM < PRESILIENT -  $\delta$  vs. H1: PCONTINUUM > PRESILIENT -  $\delta$

The sample size estimate assumes the following:

1. The acute effectiveness failure rate was approximately 10% and the TLP failure rate was 18% in the RESILIENT LifeStent® group. Thus, the success rate at 12-months post-index procedure was 72%.
2. The acute effectiveness failure rate in the CONTINUUM LifeStent® group is expected to be 1%. The TLP failure rate in the CONTINUUM LifeStent® group is expected to be equal to the RESILIENT LifeStent® group when the rates are adjusted for disease severity using the Cox's regression covariates (Rutherford Category, target lesion(s) lengths, total treated segment length and perhaps age, gender, etc.). Thus, the success rate at 12-months post-index procedure is expected to be 81%.
3. The number of subjects in the RESILIENT LifeStent® group was 134, and 112 subjects were evaluable for TLP at 12-months post-index procedure.
4. A Cox's time-to-event (survival) analysis with regression covariates will be used to estimate the survival proportions and their standard errors.
5. The Type 1 error,  $\alpha = 0.05$  (one-sided because the hypothesis is non-inferiority).
6. The Type 2 error,  $\beta \leq 0.20$  (Power =  $1 - \beta = 80\%$ ).
7. Non-inferiority margin,  $\delta = 7.5\%$ .
8. The censoring rate through 12-months post-index procedure will be 15%.

According to PASS 2008 (using the Cox's survival analysis module), the sample size required for 80% power is 252 subjects with just over 50% in one of the groups. The RESILIENT LifeStent® group has 112, so implanting 140 (56%) or more CONTINUUM LifeStent® subjects will provide at least 80% power. When this is inflated to accommodate 15% censoring through 12-months post-index procedure, the CONTINUUM sample size is 165 subjects. This sample size estimate demonstrates that secondary effectiveness (device success) is the sample-size driver for this study.

However, a minimum of 170 subjects are required to be enrolled as originally agreed upon and referenced in the FDA Post-Market Approval (PMA) Approval Order of the Bard® LifeStent® Vascular Stent (P070014). The secondary endpoint, "Device Success" demonstrated that 165 subjects are necessary to power this endpoint, including adjusting for censoring; this is very close to the 170 subjects initially stipulated by FDA. In addition to this requirement, at least 64 additional subjects treated with the 200 mm LifeStent® will be enrolled (including adjustment for censoring), which results in a minimum enrollment of 234 subjects in the study.

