#### B. Primary Effectiveness Endpoint

The primary effectiveness endpoint of the study, device success, will collectively measure both acute and chronic effectiveness.

Acute effectiveness is defined as: Successful delivery of the stent to the intended site with the post-deployment stent length being within 10% of the pre-deployment stent length.

Chronic effectiveness is defined as: Primary Target Lesion Patency (TLP) at 12-months post-index procedure, as measured by DUS. TLP is defined as the interval following the index procedure until a DUS assessment indicates that the target lesion(s) is no longer patent; that is, the treated segment has a peak systolic velocity ratio (PSR)  $\geq 2.5$ . PSR is determined by comparing velocities within the treated segment to the proximal normal arterial segment. In this study, a  $> 50\%$  stenosis is defined as a PSR of  $\geq 2.5$ .

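### The 72% and 81% device-success rates assume that no subject has both an acute and a patency failure; the documents do not support this, and the stated 80% power may be overstated

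*Combined protocol and SAP*

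**What the plan says.** Section 1.B of the SAP makes device success a composite of acute and chronic effectiveness. The acute part is "Successful delivery of the stent to the intended site with the post-deployment stent length being within 10% of the pre-deployment stent length". The chronic part is primary target lesion patency (TLP) on duplex ultrasound at 12 months.

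Section 2.C sizes the trial on non-inferiority of device success to RESILIENT and names this as the endpoint needing the largest sample.

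- Assumption 1: "The acute effectiveness failure rate was approximately 10% and the TLP failure rate was 18% in the RESILIENT LifeStent® group". It continues: "Thus, the success rate at 12-months post-index procedure was 72" per cent.
- Assumption 2: "The acute effectiveness failure rate in the CONTINUUM LifeStent® group is expected to be 1" per cent, and "The TLP failure rate in the CONTINUUM LifeStent® group is expected to be equal to the RESILIENT LifeStent® group" after covariate adjustment. It continues: "Thus, the success rate at 12-months post-index procedure is expected to be 81" per cent.
- Assumption 3: RESILIENT had 134 subjects, of whom 112 were evaluable for TLP at 12 months.
- The margin is 7.5 points. Alpha is 0.05, "one-sided because the hypothesis is non-inferiority".

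The PASS Cox module is reported to give 252 subjects in total. With 112 from RESILIENT, the plan says "implanting 140 (56%) or more CONTINUUM LifeStent® subjects will provide at least 80% power". Allowing for 15% censoring, 140 becomes 165. Minimum enrolment is 234 for other stated reasons.

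**The concern.** Both success rates are 100% minus the sum of two failure rates. That sum counts a subject with both failures twice, so it is right only if the failures never coincide. The plan's definitions do not exclude coincidence: a stent delivered to its site but off its length by more than 10% is an acute failure, yet it remains in the vessel, can be scanned, and can lose patency.

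The effect is unequal because RESILIENT is assigned ten times the acute failure rate. Overlap can raise the RESILIENT rate by up to 10 points but the CONTINUUM rate by only 1. On a common base, any overlap therefore raises the reference rate, narrows the assumed advantage and lowers power. At stake is the power claim for the endpoint that, by the plan's own account, drives the sample size.

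**Working it through.** **Inputs (SAP 2.C).** RESILIENT acute failure 0.10 and TLP failure 0.18; CONTINUUM 0.01 and 0.18; margin 0.075; one-sided alpha 0.05; 112 RESILIENT and 140 CONTINUUM evaluable; 15% censoring; minimum enrolment 234. The hazard ratio and event probability entered in PASS are not stated.

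**Reproducing the rates.** 1 − 0.10 − 0.18 = 0.72 and 1 − 0.01 − 0.18 = 0.81. Both match the plan.

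**Range on a common denominator.** Let f be the share of acute failures that also lose patency, taken as equal in both studies. Then

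- RESILIENT success = 0.72 + 0.10f, from 0.72 to 0.82
- CONTINUUM success = 0.81 + 0.01f, from 0.81 to 0.82
- advantage = 0.09 − 0.09f, from 9 points to 0

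Independence is f = 0.18: 0.90 × 0.82 = 0.738 and 0.99 × 0.82 = 0.8118, an advantage of 7.4 points.

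**Reproducing 252.** Schoenfeld form, with P_R and P_C the two success rates and Pe the event probability:

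HR = ln(P_R − 0.075) / ln(P_C)

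N = (1.645 + 0.842)² / [Pe × 0.556 × 0.444 × (ln HR)²]

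At 0.72 and 0.81, HR = ln(0.645)/ln(0.81) = 2.08 and ln HR = 0.733. Pe = 0.19 (that is, 1 − 0.81) gives N = 245 and 80.9% power at 252; Pe = 0.18 gives N = 259 and 79.0%. Both are close to the plan. Pooled event rates of 0.23 or 0.263 give 203 or 177 and do not reproduce it. So Pe = 0.18 to 0.19 is inferred, not documented. The censoring step reproduces exactly: 140/0.85 = 165.

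**Power under overlap.** Cox power = Φ(√[N × Pe × a(1 − a)] × ln HR − 1.645), where a is the CONTINUUM share. For comparison, the unpooled two-proportion power is Φ((P_C − P_R + 0.075)/SE − 1.645). About 199 evaluable corresponds to 234 × 0.85.

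| Overlap | P_R v P_C | Cox, 140 | Cox, 199 | Two-proportion, 140 | Two-proportion, 199 |
|---|---|---|---|---|---|
| None (as planned) | 72.0% v 81.0% | 79–81% | 84–86% | 92% | 95% |
| Independent | 73.8% v 81.2% | 73–75% | 79–80% | 88% | 91% |
| 30% of acute failures | 75.0% v 81.3% | 69–71% | 74–76% | 84% | 87% |
| Full | 82.0% v 82.0% | 37–39% | 41–42% | 46% | 50% |

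With Pe = 0.19, Cox power at 140 drops below 80% once about 3% of acute failures also lose patency. The two-proportion test drops below 80% only at about 39%, but it gives 74 + 93 = 167 subjects for 80% power and so is not the calculation behind 252.

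**The case against.** **The overlap is unknown.** If no RESILIENT subject had both failures, for instance because the 18% counts only patency loss as the first failure, then 72% and 81% are correct on a common base. This stands. A reader might infer that the 80% is shown to be overstated; the documents give no joint count, so they support only that it may be.

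**72% is not a strict floor.** The 72% to 82% range needs one denominator, and the plan gives both 134 and 112 without saying which rate uses which. As an illustration, suppose about 13 acute failures (10% of 134) all fall among the 112 evaluable subjects, separate from about 20 patency failures (18% of 112). Success is then (112 − 13 − 20)/112 = 70.5%. This also stands, and is itself a reason to state the denominator.

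**The power loss depends on the method.** Two-proportion power stays above 80% under independence, and enrolling 234 brings the Cox figure back to about 80%. Both are true. But the plan's stated method is Cox, and the two-proportion test does not reproduce its sample size.

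**The shift is small.** Independence moves RESILIENT by 1.8 points, against a standard error of about 4.2 points for 72% on 112 subjects (√[0.72 × 0.28/112]), and the acute rate is itself only approximate. Full overlap has no support in the documents. That is fair, but a calculation set at almost exactly 80% has little room for even a small shift.

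**False non-inferiority.** A reader might infer that a reference rate set too low makes non-inferiority too easy to declare. That would need 72% to be carried into the analysis as a fixed reference. It appears only among the sample-size assumptions; the objective refers to RESILIENT's observed device success, and assumption 4 has a Cox model estimate the proportions. No such inflation is shown.

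**Conclusion.** The point holds in a conditional form. The two success rates rest on an unstated assumption that acute and patency failures never occur in the same subject, and the plan's own definition of acute success allows them to. If the component rates share a denominator, the 9-point advantage is the most favourable these rates permit.

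Under the Cox form that approximately reproduces 252, power at 112 + 140 goes from 79–81% to 73–75% with independent failures and to 69–71% at 30% overlap. At about 199 evaluable, the independence figure is about 79–80%. These figures rest on an assumed event probability of 0.18 to 0.19 and on the same overlap share in both studies. The enrolment floor of 234 absorbs most of the independence case under Cox, but not larger overlap.

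**What to change.** In assumptions 1 and 2 of section 2.C:

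1. Replace the summed rates with RESILIENT device success counted once per subject (acute success and patent at 12 months) on one stated denominator. Derive the CONTINUUM rate on the same basis.
2. If the joint count is not available at planning, show power across RESILIENT rates of 72% to 82%, with the matching CONTINUUM rate. Give 73.8% v 81.2% as the independence case within that range. It should not be the single replacement, since independence is no better documented than exclusivity.
3. State the hazard ratio and event probability entered in PASS.
4. Restate power for 140 evaluable CONTINUUM subjects and for the planned 234 after 15% censoring.

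The cost is one tabulation of RESILIENT data, a few lines of SAP text and possibly a less favourable stated power. No extra subjects are needed.

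### Does SAP 2.C need changing because its 252-subject total cannot be rebuilt from the listed assumptions?

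*Combined protocol and SAP*

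**What the plan says.** Section 2.C of the SAP sizes the study on secondary device success, tested for non-inferiority against the RESILIENT historical control. Under "The sample size estimate assumes the following" it gives:

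- RESILIENT success 72% (10% acute failure, 18% patency failure)
- expected CONTINUUM success 81%
- 112 evaluable RESILIENT subjects
- alpha 0.05, "one-sided because the hypothesis is non-inferiority"
- 80% power, a margin of 7.5 percentage points and 15% censoring

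Item 4 says that a Cox "analysis with regression covariates will be used to estimate the survival proportions and their standard errors". The section then reports from the Cox module of the software that "the sample size required for 80% power is 252 subjects with just over 50% in one of the groups". It subtracts the 112 controls and says that 140 or more CONTINUUM "subjects will provide at least 80% power". After inflation for censoring it concludes that "165 subjects are necessary to power this endpoint, including adjusting for censoring".

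The section opens with "The protocol includes sample size considerations for the primary safety endpoint" and the other sized endpoints. Of the protocol, only the summary is among the documents reviewed.

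**The concern.** A Cox sample-size calculation takes a log hazard ratio, an overall event probability, an allocation fraction and an R-squared for the correlation of group with the covariates. The SAP gives success proportions and a margin on the proportion scale. It does not give the hazard ratio, the event rate or the R-squared, or say how 7.5 points became a hazard ratio. A reader who fills these in the obvious way gets about 200, not 252.

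One of the routes that does reach 252 uses one-sided 0.025, against item 5. If the run and the list disagree, the claims that 165 subjects are needed and that power is at least 80% would rest on inputs nobody can see. Some candidate inputs would leave power at 79% to 80% with no reserve.

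**Working it through.** **Steps that can be checked.** 252 − 112 = 140; 140/252 = 55.6%, printed as 56%; 140/0.85 = 164.7, so 165; 170 + 64 = 234. All agree with the SAP.

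**Inputs for the 252.** From section 2.C: S = 0.72 (RESILIENT), 0.81 (CONTINUUM), boundary 0.72 − 0.075 = 0.645, one-sided 0.05, 80% power. Assumed here, because not stated: hazard ratios by log-survival conversion, event rate P pooled over the two groups, R² = 0.

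- Hazard ratio under the alternative: ln 0.81 / ln 0.72 = 0.641
- Hazard ratio at the margin: ln 0.645 / ln 0.72 = 1.335
- Contrast: B = ln(1.335/0.641) = 0.733, so B² = 0.537
- (1.645 + 0.842)² = 6.183
- N = 6.183 / [P f(1−f) B² (1−R²)], with P = 0.19f + 0.28(1−f) and f the CONTINUUM fraction

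At f = 140/252, P = 0.23 and f(1−f) = 0.2469, so N = 6.183 / (0.23 × 0.2469 × 0.537) = 203. At f = 0.50, P = 0.235 and N = 196. So 252 is not reproduced on this reading.

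**Single changes of input, and power with 112 + 140.** Power is Φ(√[N P f(1−f) B² (1−R²)] − z), with z the critical value for the alpha used. The ranges cover f from 0.50 to 140/252.

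| Input | Total N | Power, 112 + 140 |
|---|---|---|
| Direct reading | 196–203 | 87.0% |
| R² = 0.2 | 245–253 | 79.8% |
| Event rate 19% | 242–245 | 80.9% |
| Event rate 18% | 256–259 | 79.0% |
| One-sided 0.025 | 249–257 | 79.2% |

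For the direct reading, 252 × 0.23 × 0.2469 × 0.537 = 7.69, and Φ(2.772 − 1.645) = 87.0%. Three of the four alternatives keep the stated alpha. With one-sided 0.025 and the simple average event rate 0.235, N is 251.9 at f = 140/252.

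**Check on the scale of the hypothesis.** The SAP's hypothesis concerns 12-month proportions. The standard error is √(0.72 × 0.28/112 + 0.81 × 0.19/140) = 0.0538. The distance from the boundary is 0.81 − 0.645 = 0.165, or 3.06 standard errors. Power is Φ(3.06 − 1.645) = 92%.

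**Planned enrolment.** 234 × 0.85 = 198.9, about 199 evaluable. With 112 + 199, N f(1−f) = 112 × 199/311 = 71.7 and pooled P = (199 × 0.19 + 112 × 0.28)/311 = 0.222. The same power formula gives 83.4% at R² = 0.2, 83.8% at an 18% event rate and 83.3% at one-sided 0.025. This assumes that all enrolled subjects enter the comparison; the SAP does not restrict it to the first 170.

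**The case for a change.** The strongest case for acting is that the SAP makes firm statements about required numbers and power, several different inputs lead to 252, and it names none of them. The analysis is explicitly covariate-adjusted. Lesion length is one of the covariates, and the study deliberately enrols lesions over 160 mm, so the R-squared between group and covariates is a real design input. At R² = 0.3 the formula gives 75% power with 112 + 140 and 79% with 112 + 199. The near-exact match at one-sided 0.025 also raises the question whether the run used the pre-specified alpha.

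What stands is that the inputs are not written down, so 252 cannot be confirmed from the SAP. What does not stand is the step from there to an error:

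- R² = 0 is the reader's choice, and it fits poorly with items 2 and 4, which call for covariate adjustment. A value near 0.2 is a natural entry.
- The 18% and 19% rates both follow from items 1 and 2. What is unlisted is their use as the overall event rate, and against the pooled rate that choice errs towards a larger sample.
- If 0.025 was entered, the sample is larger than the pre-specified 0.05 requires. The 79.2% would apply only to a test at 0.025, which the SAP does not plan.

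Nor should 87% and the two hazard ratios be written into the SAP as the correct values. Items 1 and 2 place the whole expected advantage at the procedure (10% against 1% acute failure) with equal patency failure afterwards. That is not proportional hazards, and the stated hypothesis is about proportions.

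**Conclusion.** The observation is correct as far as it goes: the list in section 2.C does not determine 252, and the R-squared, the overall event rate and the conversion of the margin are not stated. No change to the plan follows. Under the listed rates, 112 + 140 has about 87% power by the Cox formula with R² = 0 and about 92% as a comparison of proportions. Under the inputs that bring the formula near 252, it has 79% to 81%, close to the 80% claimed, and about 83% or more at the planned minimum of 234.

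The total of 252 drives neither enrolment nor analysis. The approval order fixes 170, already above 165, a further 64 bring the minimum to 234, and the non-inferiority rule uses the margin and alpha, which are both stated. The full protocol, which the SAP cites for its sample-size considerations, may hold the missing inputs.

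The conclusion rests on 15% censoring, on all enrolled subjects entering the comparison, and on an R-squared not far above 0.2. A much larger R-squared would lower power, but writing the entered value down would not alter that.

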#### **D. Assessment Schedule**

Subjects will undergo a clinical evaluation at baseline/screening (prior to index procedure), prior to hospital discharge, 30-days, and 12-, 24-, and 36-months post-procedure.

**Time and Events Schedule**

Observation	Baseline/ Screening	Intra- Procedure	Hospital Discharge	30 d (± 7d)	12 mo (± 30d)	24 & 36 mo (± 30d)
Eligibility Criteria	✓	✓				
Informed Consent	✓					
Demographics	✓					
Medical History	✓					
BUN/Creatinine and CBC	✓					
Pregnancy test HCG	✓ 					
*Concomitant Medications	✓	✓	✓	✓	✓	✓
Comprehensive Physical Exam	✓		✓	✓	✓	✓
Angiogram	✓ 	✓ 				
Resting ABI	✓		✓	✓ 	✓	✓
Rutherford (Category & Grade)	✓			✓	✓	✓
Adverse Event Assessment		✓	✓	✓	✓	✓
X-Ray (AP & lateral)					✓ 	✓ 
Color Flow Duplex Ultrasound				✓ 	✓ 	✓ 
Quality of Life Questionnaire	✓			✓	✓	✓

Perform urine pregnancy test for women who are of childbearing potential < 7 days prior to enrollment.

Baseline angiogram may be performed, 30 days prior to study enrollment or day of study enrollment just prior to intervention

Send images to Angiographic/X-Ray Core Laboratory

Only required if subject's symptoms/vascular function has worsened.

X-Ray Not Required at 36-Month Follow-Up.

Send images to Ultrasound Core Laboratory

\*Concomitant Medications; only record (anti-platelets, anti-coagulants, and direct thrombin inhibitors)

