	

– Freedom from Target Lesion Revascularization (TLR) and/or Target Vessel Revascularization (TVR) at 12-months post-index procedure.

– Secondary Device Success (compared to RESILIENT LifeStent®).

– Primary Safety of the Target Lesion Lengths > 160 mm subgroup compared to the Target Lesions treated with the 200 mm LifeStent® subgroup.

– Primary Safety of the following subgroups: 1) Target Lesion Lengths ≤ 160 mm, 2) Target Lesion Lengths > 160 mm and ≤ 240 mm, and 3) Target Lesions treated with the 200 mm LifeStent®.

– Primary Effectiveness of the Target Lesion Lengths > 160 mm subgroup compared to the Target Lesions treated with the 200 mm LifeStent® subgroup.

– Primary Effectiveness of the following subgroups: 1) Target Lesion Lengths ≤ 160 mm, 2) Target Lesion Lengths > 160 mm and ≤ 240 mm, and 3) Target Lesions treated with the 200 mm LifeStent®.

– Freedom from Fracture (FFF) at 12- and 24-months post-index procedure.

– Primary TLP (Sustained and Expanded) for Target Lesion Lengths > 160 mm at 12-, 24- and 36-months post-index procedure.

– Freedom from TLR and/or TVR for Target Lesion Lengths > 160 mm at 12-, 24-, and 36-months post-index procedure.

– Secondary Safety defined as freedom from death (excluding 30-days and 12-months post-index procedure), stroke, myocardial infarction (MI), emergent surgical revascularization, significant distal embolization in target limb, target limb major amputation, and thrombosis of target vessel at 30-days and 12-, 24-, and 36-months post-index procedure.

– Acute Technical Success defined as successful deployment of the stent to the intended location.

– Acute Lesion Success defined as attainment of ≤ 30% residual stenosis of the target lesion using any percutaneous method and/or non-investigational device (i.e., post-dilatation).

– Acute Procedure Success defined as lesion success and no periprocedural complications (death, stroke, MI, emergent surgical revascularization, significant distal embolization in target limb, and thrombosis of target vessel).

– Sustained Freedom from TLR and/or TVR at 24- and 36-months post-index procedure

– Sustained Hemodynamic Success defined as sustained improvement of Ankle-Brachial Index (ABI) from baseline value of ≥ 0.15 at 30-days and 12-, 24-, and 36-months post-index procedure without the need for repeated TLR in surviving subjects.

– Sustained Clinical Success defined as sustained cumulative improvement from baseline value of ≥ 1 category according to Rutherford et al at 30-days and 12-, 24-, and 36-months post-index procedure without the need for repeated TLR in surviving subjects.

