13. **Acute Procedure Success** defined as lesion success and no peri-procedural complications (death, stroke, MI, emergent surgical revascularization, significant distal embolization in target limb, and thrombosis of target vessel).
14. **Sustained Freedom from TLR and/or TVR** at 24- and 36-months post-index procedure.
15. **Sustained Hemodynamic Success** defined as sustained improvement of Ankle-Brachial Index (ABI) from baseline value of  $\geq 0.15$  at 30-days and 12-, 24-, and 36-months post-index procedure without the need for repeated TLR in surviving subjects.
16. **Sustained Clinical Success** defined as sustained cumulative improvement from baseline value of  $\geq 1$  category according to Rutherford et al. at 30-days and 12-, 24-, and 36-months post-index procedure without the need for repeated TLR in surviving subjects.
17. **Sustained TLP** at 24- and 36-months post-index procedure corresponding to PSR  $< 2.5$ .
18. **Expanded TLP** at 12-, 24- and 36-months post-index procedure corresponding to PSR  $< 3.0$ .
19. **Cumulative (primary-assisted and secondary) TLP** at 12-, 24-, and 36-months post-index procedure corresponding to PSR  $< 2.5$  and PSR  $< 3.0$ .
20. **Quality of Life** as assessed by Walking Impairment Questionnaire (WIQ) at baseline, 30-days and 12-, 24- and 36-months post-index procedure.

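### Sustained Hemodynamic Success is to be reported at 30 days in survivors, but the schedule requires a 30-day ABI only in subjects who have worsened

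*Combined protocol and SAP*

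**What the plan says.** The Protocol Summary lists "Sustained Hemodynamic Success defined as sustained improvement of Ankle-Brachial Index (ABI) from baseline value of ≥ 0.15 at 30-days and 12-, 24-, and 36-months" among the secondary endpoints. SAP section 1.C, item 15, gives the same definition and closes it with "at 30-days and 12-, 24-, and 36-months post-index procedure without the need for repeated TLR in surviving subjects". So 30 days is a named reporting time, and the population is survivors, not a tested subset.

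The Time and Events Schedule (SAP section 2.D) ticks resting ABI at baseline, discharge, 30 days, 12 months, and 24 and 36 months. Only the 30-day tick has a footnote, number 4: "Only required if subject's symptoms/vascular function has worsened". The footnote does not say against which visit, or by how much, a subject must have worsened.

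The 30-day visit itself is for everyone. Section 2.A states: "Clinical follow-up for all subjects will be performed at hospital discharge, 30-days and 12-, 24-, and 36-months post-procedure". At that visit the Rutherford category, the adverse event assessment and the quality of life questionnaire are ticked without condition.

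**The concern.** The endpoint needs a 30-day ABI in every survivor, and the schedule guarantees one only in subjects who are doing worse. The gap comes from the schedule and not from missed visits, and what triggers the test is closely related to the outcome. A 30-day success rate among measured subjects would then give too much weight to likely failures.

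The rest of the plan suggests an oversight. Item 16, Sustained Clinical Success, is the parallel endpoint ("sustained cumulative improvement from baseline value of" at least one Rutherford category). It names the same visits, and its 30-day measure is unconditional. Footnote 5 drops the 36-month X-ray, and the fracture endpoint (item 7) accordingly stops at 24 months. Item 15 lacks this match between endpoint and schedule.

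At stake is the 30-day rate of one of 20 secondary endpoints. The later rates are also at stake if sustained success means success at every earlier visit, because 30-day losses would then be looked for mainly in subjects who had worsened.

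**Working it through.** The plan states no rate, power or sample size for item 15, so there is no figure of its own to reproduce. A simple selection model shows the direction and what the size depends on.

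**Inputs**

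- N = 234, the minimum enrolment (Protocol Summary; SAP section 2.B). Early deaths are ignored.
- w = share of subjects who have worsened at 30 days, all measured. Assumed 5%, 10% or 20%.
- s_w = success in worsened subjects. Assumed 20% or 40%.
- s_o = success in the others. Assumed 80%.
- u = share of the others who have an optional 30-day ABI, taken as unrelated to outcome within that group. Not in the documents, so varied from 0 to 1.

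**Required measurements.** 234 × 0.05 = 11.7 and 234 × 0.20 = 46.8, so about 12 to 47 subjects would have a required 30-day ABI.

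**Formulas**

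- True rate = w·s_w + (1−w)·s_o
- Rate among measured = [w·s_w + (1−w)·u·s_o] / [w + (1−w)·u]
- Error = −(s_o − s_w) × [w/(w + (1−w)·u) − w]

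The error is negative whenever s_w < s_o and u < 1, and zero when u = 1.

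**Worked case: w = 0.10, s_w = 0.20, s_o = 0.80, u = 0.50**

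- True: 0.02 + 0.72 = 0.740
- Measured: (0.02 + 0.36) / (0.10 + 0.45) = 0.38/0.55 = 0.691
- Error: −4.9 points

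**Range over the assumed w and s_w, with s_o = 80%**

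| Share of others tested (u) | Smallest error (w = 5%, s_w = 40%; at u = 0, w = 20%) | Largest error (w = 20%, s_w = 20%; at u = 0, w = 5%) |
|---|---|---|
| 0 | 0.40 × 0.80 = −32.0 points | 0.60 × 0.95 = −57.0 points |
| 0.25 | 0.40 × (0.1739 − 0.05) = −5.0 | 0.60 × (0.50 − 0.20) = −18.0 |
| 0.50 | 0.40 × (0.0952 − 0.05) = −1.8 | 0.60 × (0.3333 − 0.20) = −8.0 |
| 0.75 | 0.40 × (0.0656 − 0.05) = −0.6 | 0.60 × (0.25 − 0.20) = −3.0 |
| 1 | 0 | 0 |

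**Sensitivity to the assumed rates at u = 0.50.** With s_o between 70% and 90%, the error is −1.4 to −9.3 points. With s_w at 0–30% and s_o at 70–80%, it is −1.8 to −10.7 points.

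**Other rules for untested subjects, same worked case**

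- Counted as successes: 0.38 + 0.45 = 0.83, error +9.0 points.
- Counted as failures: 0.38, error −36.0 points.
- Discharge ABI carried forward, if discharge and 30-day success differ by an assumed 5 points in untested subjects: ±0.90 × 0.50 × 5 = ±2.25 points.

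The direction therefore depends on the handling rule as well as on the schedule.

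**The case against.** The strongest reply is that the downward bias belongs to an analysis the plan does not name. The supplied text ends at the schedule and specifies neither a rate among measured subjects nor any alternative. Counting untested subjects as successes would push the rate up. This stands. A reader might infer that the plan commits itself to an understated 30-day rate, or that it wrongly omits a missing-data rule; the documents support neither reading. What they do show is that the endpoint and the schedule disagree.

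Second, the footnote limits what is required and forbids nothing. If sites take a 30-day ABI in everyone, the error is zero. The 32 to 57 points at u = 0 describe an extreme and should not be read as the expected error. This also stands.

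Third, worsened is undefined. A subject who is worse than at discharge may still be 0.15 above baseline. So the lower success rate in worsened subjects is an assumption, though a very plausible one.

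Fourth, the discharge ABI is scheduled for all, and the footnote could be read as a retest only when something has changed. With carry-forward the error may be small. But no passage states carry-forward, and item 15 names 30 days and not discharge.

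Finally, this is a secondary endpoint. It is outside the historical-control comparisons (SAP section 1) and the sample-size considerations (section 2.C). That limits the weight of the point but does not remove the contradiction.

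**Conclusion.** The point holds as a contradiction between endpoint and schedule. Followed as written, the plan guarantees 30-day ABI data only in a subset selected on something close to the outcome, while item 15 promises a 30-day result in survivors.

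A rate among measured subjects would be biased downward on two conditions: worsened subjects reach the 0.15 gain less often, and some of the others go untested. The size cannot be found from the documents. It is zero with full testing and about 2 to 8 points with half of the others tested, and every rate behind that range is assumed.

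The 12-, 24- and 36-month results may also be affected, but only if sustained success requires success at each earlier visit, which the definition does not make clear. It would be wrong to infer any effect on the primary endpoints, the comparisons with RESILIENT or the sample size, because none of them uses the 30-day ABI. The plan should be corrected, but no main conclusion depends on it.

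**What to change.** Reconcile item 15, in the Protocol Summary and in SAP section 1.C, with footnote 4, without adding a procedure:

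1. Remove 30 days as a reporting time for the item 15 rate, and base the rate on the unconditionally scheduled ABIs at 12, 24 and 36 months.
2. Report measured 30-day ABIs descriptively, labelled as selected for worsening. Show the already scheduled discharge ABI as the early descriptive value.
3. Count an untested 30-day ABI as neither success nor failure.
4. Add a sensitivity analysis of the sustained rate in which measured 30-day losses count as failures. Those losses are real under the endpoint's definition, but whether they are found depends on who is tested, so they should be visible without driving the main rate.

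The cost is a change of wording in two places, one table label and one sensitivity analysis. The downside is that there is no 30-day hemodynamic success rate, and a 30-day loss that recovers by 12 months appears only in the descriptive table and the sensitivity analysis.

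If the sponsor needs to keep a 30-day rate, the condition in footnote 4 would have to go instead. Under the assumed 5–20% worsening, that means up to 234 × 0.80 = 187 to 234 × 0.95 = 222 further resting ABIs, at a visit that already takes place.
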